Background: In recent years, various methodologies have been introduced to enhance the outcomes of scaling and root planing (SRP), with the intent of potentially eliminating the necessity for periodontal surgical interventions under specific circumstances. Noteworthy among these novel approaches are the utilization of non-steroidal anti-inflammatory drugs (NSAIDs) and herbal remedies like Aloe Vera. This present study endeavors to clinically assess the impact of flurbiprofen gel in contrast to Aloe Vera gel, as supplementary agents to SRP, in the elimination of periodontal pocket depths among individuals afflicted by stage III chronic periodontitis, particularly focusing on the subset of smoking patients. **Materials and Methods:** In this study, 60 patients with stage III/grade C periodontitis were enrolled. They were divided into three groups using the split mouth method: Group one (G1), which received Flurbiprofen and placebo, Group two (G2), which received Aloe Vera and placebo, and Group three (G3), which received Flurbiprofen and Aloe Vera. At the baseline, the fourth, eighth-, twelfth weeks and six months following treatment, the plaque index (PI), gingival index (GI), bleeding on probing (BOP), clinical attachment level (CAL), and probing depth (PD) were all measured. **Statistical Analysis:** Statistical analysis was done using SAS 9.4 Software (SAS Institute Inc., Cary, NC, USA). Means and standard deviations (SD) were calculated for all continuous variables (periodontal parameters: CAL, PD, BOP, GI, PI) at the baseline, fourth week, eighth week, and twelfth week and 6 months.

Keywords: periodontitis, flurbiprofen, aloe vera, root planing.

Introduction:

Inflammation and periodontal tissue destruction is a consequence of periodontal pockets originating from chronic periodontitis. [1] The latter is an infectious disease resulting from the interaction between the invasion of biofilm microorganisms and periodontal immune response in a vulnerable host. [2]

During periodontal attachment loss, PGE2 production levels primarily by macrophages and fibroblasts are increased in the tissues and gingival crevicular fluid (GCF). [3,4] PGE2 promotes the release of MMPs, in addition to osteoclastic bone resorption, and it play a significant role in the alveolar bone loss observed in periodontitis. [5]

Smoking has been identified as a major risk factor in the development and progression of periodontal disease. Epidemiological studies have presented a significantly higher risk for periodontal disease in smokers compared to non-smokers, and the increased risk is proportional to the duration and rate of smoking (Eke et al., 2016).[6]

The first main goal during the treatment of periodontal disease is eliminating microbial source and causative factors, thus preventing further progression of the disease and maintaining periodontal tissue health. [7] Surgical and non-surgical modalities are available for the treatment of periodontal diseases. [7] The non-surgical option consisting of mechanical debridement of the tooth surface with scaling and root planning (SRP), [8] improves pocket depth (PD) and increases clinical attachment level (CAL) to some extent, [9]

However, mechanical debridement alone may not be enough in patients with deep periodontal PD or having areas of furcation involvements. [10] Some pathogens like *Actinobacillus actinomycetemcomitans*, *Porphyromonas gingivalis*, *Prevotella Intermedia*, *Bacteroides forsythus*, *peptostreptococci* micros may not be eliminated as a result of the limited access in deep subgingival areas, thus increasing the risk of treatment failure. [10]

Research have shown the significance of PGE2 in the development of periodontal diseases, [11]and since prostaglandins are inhibited by nonsteroidal anti-inflammatory drugs (NSAIDs), [12] researchers have explored the possible use of NSAIDs as possible host–response modulators in the treatment of periodontal disease.[13] However, achieving noticeable periodontal improvements requires daily administration of NSAIDs for extended periods which may lead to undesirable side effects gastrointestinal (GI), renal, cardiovascular (CV), cerebrovascular, and central nervous system (CNS) adverse effects [14]

It is advised to consider using local drug delivery (LDD) as an adjunct to conventional periodontal therapy to reach the best clinical outcomes. LDD is an effective method of delivering drugs. Higher drug concentrations at the targeted area can be reached using LDD with a lower drug dose than the usual systemic delivery and thus fewer side effects. [15]

A topic that seems of particular interest is the development local NSAID formulations (e.g., gels, toothpaste, and rinses) with daily usage. These products may lead to an improvement in the reduction of detrimental systemic effects of non-selective NSAIDs in the long-term host modulation of periodontitis-susceptible patients. [16] Moreover, studies demonstrated that prostaglandin production inhibitors, like NSAIDs, can affect bone loss in periodontal disease. [17]

The available data suggests that when flurbiprofen, an NSAID, is delivered locally through gel media during SRP, it enhances the benefits of the latter treatment and expedites the resolution of inflammation [18].

Numerous adjunctive therapies to SRP have been explored in the field of periodontics. Among these, laser treatment [19], topical and systemic antibiotics like azithromycin [20] and clarithromycin [21], as well as chemicals such as hyaluronic acid [22] and various antiseptic and anti-inflammatory agents with immunomodulatory properties [19,23], have been documented to offer potential advantages.[24]

Herbal products have gained preference over conventional drugs due to their considerable natural efficacy, enhanced safety profile, and cost-effectiveness. Conversely, modern pharmaceuticals are associated with various adverse effects. Prolonged use of these drugs has, at times, led to antibiotic resistance, prompting a gradual integration of herbal medicines as dietary supplements to address prevalent human health and oral issues.[25]

Numerous natural/herbal medications, including green tea and *salvadora persica*, have been the subject of investigation as potential adjuncts to SRP for the management of periodontal diseases, offering the advantage of reduced side effects [26,27].

Among these herbal options, Aloe Vera, a cactus-like plant belonging to the Liliaceae family, stands out with its rich composition of approximately 360 species, containing 75 active ingredients such as vitamins, enzymes, minerals, lignins, sugars, saponins, amino acids, and salicylic acids [28]. In vitro and animal model studies have demonstrated medicinal effects of Aloe Vera, encompassing anti-inflammatory, anti-arthritic, and anti-bacterial properties [28-29]. Moreover, the treatment effects of Aloe Vera on systemic disease such as cancers, regulation of blood glucose levels, wound and infection healing have been investigated in some studies. [28-

30] Aloe Vera also inhibits the cyclooxygenase pathway, dropping the production of prostaglandins, thus decreasing the inflammation. [31]

Some studies stated the use of aloe Vera in dentistry in numerous areas like disinfecting dental unit water network, [32] gutta-percha sterilization, [33] antiseptic effect on candida albicans, [34] Aphthous stomatitis management, [35] as an ingredient in toothpastes [36-37] and mouthwashes.[28] Up to date, limited studies have been reported in relation to the effect of topical application of aloe Vera in the periodontal pocket for periodontal disease management. [38]

The null hypothesis is that flurbiprofen has no statistically significant effect in comparison to Aloe Vera gel as an adjunctive to SRP in the reduction of periodontal pockets in smoking patients with chronic periodontitis stage III.

Aim of this study:

This study aims to evaluate clinically the effect of flurbiprofen gel in comparison to Aloe Vera gel as adjunctive to SRP in the reduction of periodontal pockets in patients with chronic periodontitis stage III in smoking patients.

Materials and methods:

Participants:

This study was conducted at the Department of Oral Surgical Sciences, Division of Periodontology, Faculty of dentistry, Beirut Arab University (BAU)-Lebanon after approval of Institutional Review Board (IRB) with trial NO 2022-H-0100-D-R-0487. Patients were first briefed about the study and written consent was obtained. The study was performed in compliance with the principles of the Declaration of Helsinki.

The estimated sample size will be calculated according to <http://epitools.ausvet.com.au/>, by taking the means of clinical attachment level at 3 months in both groups from a previous similar study conducted by (39) where mean for test site = 5.75 ± 0.35 and mean for control site is = 6.4 ± 0.3 , where the variance will be calculated to be 0.35, assuming a confidence level of 95% and a study power of 80%. The calculated sample size will be 14 patients per group (28 operating sites). However, as some dropouts may be expected, a minimum of 20 patients per group were recruited

Inclusion criteria: 60 patients were selected who had clinical periodontal loss and radiographic bone loss of stage III/grade C with no history of systemic disease. They had at least 2 periodontal sites with a pocket depth of six mm or greater, radiographic evidence of bone loss extending to the middle third of the root, and clinical attachment loss of five mm or more. Eligible subjects were categorized as current smokers if they consistently smoked more than 10 cigarettes per day for a minimum of 5 years. Additionally, individuals with no record of undergoing any periodontal treatment within the six months preceding the study were considered for inclusion. These stringent criteria aimed to ensure a relevant and homogeneous patient cohort for the research investigation.

Exclusion criteria: Patients with systemic illnesses such as diabetes mellitus or conditions that could potentially impair wound healing were excluded from participation. Additionally, individuals who were pregnant or lactating were not considered for inclusion in the study. Subjects who had been prescribed systemic antibiotics or non-steroidal anti-inflammatory drugs (NSAIDs) within the three months preceding the study were also excluded. Furthermore, individuals with confirmed or suspected hypersensitivity to Flurbiprofen or aloe Vera, the focus of the investigation, were not included in the study population. These stringent exclusion criteria aimed to control for potential confounding factors and establish a well-defined and relevant patient group for the research analysis.

Clinical protocol

Initial therapy was performed on all patients and consisted of full mouth scaling and root planing on 2-4 sessions, by hand and ultrasonic instrumentation, with oral hygiene instructions reinforcement and proper brushing technique (modified Bass technique) instructions. Note that patients received the same toothbrushes, toothpaste, and interdental brushes. Oral hygiene was reinforced at every visit.

The selected patients were allocated into three groups (each containing 20) with the help of a computerized randomizer (Randomizer.org), and using a split mouth design, sites were randomly allocated for each patient into either test or control group using a coin flip method:

- Group one (G1): comprised of 20 patients who received treatment involving the application of flurbiprofen gel as an adjunct to scaling and root planing. Specifically, on the test site of each patient, one milliliter of 2.5% flurbiprofen gel was applied, while on the contralateral side, scaling and root planing were performed as the control intervention.
- Group two (G2): comprised of 20 patients who received treatment involving the application of aloe Vera gel as an adjunct to scaling and root planing. Specifically, on the

test site of each patient, one milliliter of 98% aloe Vera was applied, while on the contralateral side, scaling and root planing were performed as the control intervention.

- Group three (G3): The intervention involved applying flurbiprofen gel on one site, while the contralateral side received an application of 98% aloe vera.

Clinical measurements:

The clinical periodontal parameters were recorded by one blinded examiner from the mesio-buccal, mid-buccal, disto-buccal, disto-lingual, mid-lingual, and mesio-lingual surfaces of each tooth using a colour coded periodontal probe (PQWBR - Hu Friedy Mfg. Inc. Chicago, IL, USA): and checked by another blinded examiner. Examiners were calibrated to ensure intra-examiner as well as inter-examiner agreement when measuring PD and CAL values. Fifteen patients were examined twice before the trial, 24 hours apart. Calibration was considered accepted if both measurements at the baseline and after 24 hours were similar to one mm at the 90% level.

In this clinical study, various clinical measurements were undertaken to assess the oral health status of the participants. These measurements included the clinical attachment level (CAL), probing depth (PD), plaque index (PI), gingival index (GI), and bleeding on probing (BOP).

Initially, the PI and GI were measured at four sites per tooth, with gingival bleeding being recorded within 15 seconds. To prevent misinterpretation of gingival bleeding as BOP, patients were asked to rinse with water after this assessment. Subsequently, all teeth were probed at six different locations per tooth. CAL was determined as the distance from the cemento-enamel junction (CEJ) to the pocket depth, while the PD was measured as the distance from the gingival margin to the base of the pocket. BOP was recorded 15 seconds after probing. It is important to note that these clinical parameters were recorded at the baseline (1st visit) before the treatment and were repeated at the fourth week (2nd visit), eighth week (3rd visit), twelfth week (fourth visit), and at 6 months (5th visit). During this observation period, participants received reinforcement of plaque control and additional instructions to maintain optimal oral hygiene

Preparation of gels:

Aloe Vera:

Aloe vera gel used in this study was 98% aloe vera[®] gel concentration (Avivir; Denmark) and 2% normal saline. Commercial preparation method of 98% concentration of aloe vera gel was washing the ripe aloe Vera leaves thoroughly under water and cutting off their skin. Each leaf was cut into several pieces and seeping gel from the pieces were collected in a sterile container and stored at 4°C until the time of application. [38]

Flurbiprofen:

Gel was made of 20% poloxamer and 10% ethanol as an Optimum formulation with sustained release up to 48 hours and a reasonable sol gel transition phase.

Statistical analysis:

Statistical analysis was done using SAS 9.4 Software (SAS Institute Inc., Cary, NC, USA). Means and standard deviations (SD) were calculated for all continuous variables (periodontal parameters: CAL, PD, BOP, GI, PI) at the baseline, fourth week, eighth week, and twelfth week and 6 months. Repeated linear mixed-effects models (PROC MIXED in SAS) were used to examine the changes in all periodontal parameters over the five-time points within each group and between groups. An unstructured covariance matrix was used, residual plots were visually reviewed to check model fit, and extreme outliers were eliminated using the restricted likelihood distance. A Tukey-Kramer 8 correction was applied to all pairwise comparisons. One-way ANOVA was used to examine group differences in PD reduction and CAL. A p-value of 0.05 was considered statistically significant.

References:

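### The 80% power was calculated for attachment level at test versus control sites, not for flurbiprofen versus aloe vera on pocket reduction, and the variance of 0.35 behind it needs a label or a source

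*Combined protocol and SAP*

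**What the plan says.** The null hypothesis, at the end of the Introduction, is that "flurbiprofen has no statistically significant effect in comparison to Aloe Vera gel as an adjunctive to SRP in the reduction of periodontal pockets". The aim repeats the same comparison and outcome.

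The only sample-size calculation is under Materials and methods, Participants. It proceeds "by taking the means of clinical attachment level at 3 months in both groups from a previous similar study", which the reference list (item 39) shows to be a study of locally delivered minocycline in smokers. The two site values are "mean for test site = 5.75 ± 0.35 and mean for control site is = 6.4 ± 0.3". Neither ± figure is labelled as an SD, a standard error or a variance. The remaining inputs come later in the same sentence, "where the variance will be calculated to be 0.35, assuming a confidence level of 95% and a study power of 80" per cent. The result is "The calculated sample size will be 14 patients per group (28 operating sites"), and because dropouts were expected, "a minimum of 20 patients per group were recruited".

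Under Clinical protocol, patients are randomised to three groups of 20, and within patients "sites were randomly allocated for each patient into either test or control group using a coin flip method". G1 compares flurbiprofen with scaling and root planing alone, and G2 compares aloe vera with the same control. In G3, "The intervention involved applying flurbiprofen gel on one site, while the contralateral side received an application of 98% aloe vera".

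The Statistical analysis section plans mixed models over five time points, a Tukey-Kramer correction for pairwise comparisons, and a one-way ANOVA for probing-depth (PD) reduction and CAL. It gives no effect size or power.

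**The concern.** The powered contrast and the hypothesis differ in three ways: the comparison (active versus control site, against one gel versus the other), the outcome (CAL, against pocket reduction) and the agent (minocycline, against the two trial gels). Two active adjuncts need not differ by as much as an active site differs from a control site, and the plan does not say what difference it expects between them. If the gel comparison is not significant, a reader may take it as no difference, shown with 80% power. That power was never calculated.

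The variance is a smaller matter. It is described as calculated, yet it equals the number printed after ± for the test site, and no calculation is shown. If that number is an SD, it was entered without being squared, and the stated power is not the power of the stated design.

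**Working it through.** **Inputs.** From the Participants paragraph: means 5.75 and 6.4, so the difference is 6.4 − 5.75 = 0.65 mm; ± values 0.35 and 0.3, unlabelled; variance 0.35; 95% confidence; 80% power; 14 per group calculated and 20 recruited. Sidedness is not stated; two-sided 5% is assumed here.

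**Step 1: reproduce the plan's figure.** Two independent means, normal approximation:

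n per group = 2 × variance × (1.960 + 0.842)² / 0.65²

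With variance 0.35, n = 13.004, rounded up to 14. The stated size is reproduced. Exact two-sample t power at 14 is 79.9%, which agrees with the stated 80%.

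**Step 2: what the ± values imply for the variance.**

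| Reading of ± | Variance | n by the same formula | Exact power at 14 per group |
|---|---|---|---|
| SD, test site | 0.35² = 0.1225 | 4.55, so 5 | 99.7% |
| SD, mean of both sites | (0.1225 + 0.09)/2 = 0.106 | 3.95, so 4 | 99.9% |
| Variance, larger value | 0.35 | 13.004, so 14 | 79.9% |
| Variance, mean of both sites | (0.35 + 0.30)/2 = 0.325 | 12.08, so 13 | above 79.9% |
| Standard error | needs the earlier study's n, not given | – | – |

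So 0.35 does not come from averaging the printed values on either the SD or the variance reading. On both, it is at least as large as the variance the values imply.

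**Step 3: is the CAL contrast at risk?** Test and control sites lie in the same mouth, so a paired t test is the closer check. The SD of the within-patient difference is √(2 × variance × (1 − ρ)). The correlation ρ is not in the documents and is assumed to lie between 0 and 0.5. For 0.65 mm:

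- Variance 0.35: 77% to 97% at 14 pairs, 91% to 99.6% at 20.
- Variance 0.1225: above 99% at either number.

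**Step 4: what can be said about flurbiprofen versus aloe vera?** The two gels meet within patients only in G3 (20 patients). G1 versus G2 test sites is a between-patient comparison, 20 against 20. With no SD for PD reduction in the documents, detectable differences can be given only in SD units (two-sided 5%, 80% power, unadjusted t tests):

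- G3: 0.66 × SD of the within-patient difference at 20 pairs, and 0.81 × at 14 completing pairs.
- G1 versus G2: 0.91 × the between-patient SD at 20 per group, and more with dropout.

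The Tukey-Kramer correction makes these larger. By how much depends on the family of comparisons, which the plan does not define.

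As illustration only, borrow an SD between 0.35 and √0.35 = 0.592 from the CAL levels and take ρ from 0.5 to 0. The SD of the difference then runs from 0.35 to 0.592 × √2 = 0.837. The G3 detectable difference is 0.23 to 0.55 mm at 20 pairs (0.66 × 0.35 and 0.66 × 0.837) and 0.28 to 0.68 mm at 14 (0.81 × the same).

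**The case against.** The strongest reply is that the arithmetic is right and the size covers every group. The paragraph sizes each group, and the Clinical protocol section places all three under one split-mouth allocation, so G3 has a stated size. If 0.65 mm and variance 0.35 are carried over to G3, its 20 pairs give 91% to 99.6% power for ρ from 0 to 0.5. This stands: it would be wrong to say that G3 was never sized. What remains is that nothing ties a 0.65 mm active-versus-control difference in CAL to two active gels or to PD reduction. Whether 0.65 mm is too large for them cannot be settled from the documents.

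Second, CAL and PD reduction are both analysed and no primary endpoint is named in these sections, so sizing on CAL is not in itself a contradiction. That is fair. The gap lies between the power statement and the hypothesis, which names pocket reduction.

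Third, a planning variance may be set above the squared SD on purpose, and the plan never claims 80% power for the gel comparison. Both are true. They make this a matter of sourcing and of interpretation, not of a wrong sample size.

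A reader might infer that the variance slip leaves the trial too small. The documents do not support that: on the SD and variance readings the printed value is conservative. Only the standard-error reading leaves the question open.

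**Conclusion.** The point holds in a limited form. The 80% applies to a 0.65 mm CAL difference at 3 months, test versus control site, under variance 0.35. It is not a power for flurbiprofen versus aloe vera on pocket reduction, for which the plan gives neither a target difference nor an SD. This should be corrected because it bears directly on how a non-significant gel comparison is read.

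The variance point is secondary. The 14 per group follows from the printed input. If the ± values are SDs, the stated power is too low (above 99% at 14, not 80%). If they are variances, averaging changes 14 to 13. If they are standard errors, nothing can be derived.

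The documents do not support the stronger conclusions that the CAL contrast is underpowered or that the gel comparison must be. The second depends on a difference and an SD that are not given. The paired figures rest on the assumed correlations, and the detectable differences on unadjusted t tests that are not the planned analysis.

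**What to change.** 1. In the sample-size paragraph, state that the 80% power applies only to CAL, test versus control site, under variance 0.35, and that it is not a power for flurbiprofen versus aloe vera.
2. In the Statistical analysis section, commit to reporting the flurbiprofen-minus-aloe difference in PD reduction with its 95% confidence interval, within patients in G3 and between patients for G1 versus G2. Say that a non-significant result will not be read as equivalence.
3. Correct or source the variance. Label the ± values. If they are SDs, give the variance as about 0.106 and the power at 14 per group as above 99%. If 0.35 was chosen deliberately, say so and give its basis.
4. If a detectable difference for G3 is quoted, give it as a range over completing pairs (0.66 to 0.81 times the SD of the within-patient difference for 20 down to 14 pairs, unadjusted paired t). Describe it only as larger after the Tukey-Kramer correction.

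The cost is a few sentences and one extra reported interval for each comparison. Enrolment, design and data collection do not change.

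### The entry rule asks for two sites of 6 mm or more anywhere in the mouth, so it does not guarantee a qualifying site on each side for the split-mouth pair

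*Combined protocol and SAP*

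**What the plan says.** Inclusion criteria: patients had "at least 2 periodontal sites with a pocket depth of six mm or greater". The same section requires "clinical attachment loss of five mm or more" and radiographic bone loss. None of these conditions mentions side, quadrant or tooth.

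Clinical protocol: "using a split mouth design, sites were randomly allocated for each patient into either test or control group using a coin flip method". For Groups one and two, "on the contralateral side, scaling and root planing were performed as the control intervention". For Group three, "the contralateral side received an application of 98% aloe vera".

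Clinical measurements: six locations are probed on every tooth, so a single tooth can contribute more than one deep site.

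Participants (sample size): 14 patients are counted as 28 operating sites, which is two per patient, and recruitment was raised to 20 per group for dropout.

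Statistical analysis: mixed models follow all parameters over five visits, baseline included. One-way ANOVA is used for group differences in PD reduction and in CAL. No baseline covariate is named.

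**The concern.** The design compares a treated site with one on the opposite side of the same mouth. It therefore needs one suitable pocket on each side. The entry rule counts deep sites without regard to where they are, so a patient can meet it and still have no site of 6 mm or more on one side. The investigator must then use a contralateral site below the study's threshold, treat two sites on the same side contrary to the group descriptions, or lose the patient's contrast after randomisation.

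A deep pocket and a shallow one do not have the same room to improve. Unequal pairs add variance to the within-mouth difference and, with 20 patients per group, can leave a chance imbalance at baseline. With one site per treatment per patient, an unsuitable site weakens or removes that patient's whole contribution.

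**Working it through.** **1. Text.** The sections set side by side:

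| Section | Requirement | Side condition |
|---|---|---|
| Inclusion criteria | at least 2 sites, PD 6 mm or more | none |
| Clinical measurements | six locations per tooth | none; two sites may share a tooth |
| Clinical protocol, all groups | test or first gel on one side, comparator on the other | contralateral |

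No section requires a qualifying site on each side, defines the pair, or says how the study site is chosen when a side has several qualifying sites or none.

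**2. The plan's own sample size.** Inputs from Participants: difference 6.4 − 5.75 = 0.65 mm (CAL at 3 months), variance 0.35, 95% confidence, 80% power. For two independent means, two-sided:

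n = 2 × 0.35 × (1.960 + 0.842)² / 0.65² = 13.004, rounded up to 14.

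This matches the stated 14. The point made here does not dispute that figure.

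**3. If unmatched patients are unusable (illustration).** The share without a qualifying pair is assumed. Power = Φ(0.65 / √(2 × 0.35 / n) − 1.960), with n the usable pairs out of 20:

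| Share without a pair | Usable pairs | Power |
|---|---|---|
| 0% | 20 | 93.5% |
| 10% | 18 | 90.9% |
| 20% | 16 | 87.4% |
| 30% | 14 | 82.8% |
| 40% | 12 | 76.8% |
| 50% | 10 | 69.0% |

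The margin from 14 to 20 is used up at 30%, before any real dropout.

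**4. If unmatched patients are kept (illustration).** Assumptions not in the documents: within-patient correlation 0.5; 25% of pairs mismatched by g mm in random direction; a fraction s of the gap carried into the outcome. The analysis is a paired t test with 20 pairs (19 df) and a 0.65 mm effect.

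Variance of the difference = 2 × 0.35 × (1 − 0.5) + 0.25 × (s × g)² = 0.35 + 0.25 × (s × g)².
Noncentrality = 0.65 / √(variance / 20).

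Matched pairs: variance 0.35, noncentrality 4.91, power 99.6%.

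| Carried through (s) | g = 1 mm | g = 2 mm | g = 3 mm |
|---|---|---|---|
| 0.3 | 99.5% | 98.6% | 96.0% |
| 0.5 | 99.0% | 94.5% | 82.3% |
| 1.0 | 94.5% | 66.1% | 40.2% |

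Example for s = 0.5, g = 3: 0.35 + 0.25 × 2.25 = 0.9125; 0.65 / √(0.9125 / 20) = 3.04; power 82.3%.

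With correlation 0 the first term becomes 0.70. Matched power is then 90.9%, and the s = 0.5 row becomes 88.4%, 80.8% and 69.0%.

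The row for s = 1.0 treats the follow-up value as if baseline were never used. The planned analysis looks at change over visits and at PD reduction, so a partial carry-through is the more suitable illustration. CAL is less clear, because the ANOVA sentence does not say whether CAL is a change or a level. The model also puts a PD gap on a CAL scale, so it indicates scale only.

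**The case against.** The best reply is that the text, read as a whole, already implies one deep site per side. The minimum of two sites matches the two treatments, the sample-size section counts two operating sites per patient, and the comparator is placed contralaterally. On this reading only an explicit statement of side is missing. That is a fair account of what was probably intended. But the split-mouth wording implies at most that a contralateral site is used. It sets no depth for that site, and the one sentence that sets a depth is silent on side.

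A second reply is that the problem may be rare, and this stands. If qualifying sites fell left or right independently with equal chance, all k of them would lie on one side with probability 2 × 0.5^k: 50% for two sites, 12.5% for four, 3.1% for six. These are heavy smokers with stage III/grade C disease, and two sites is a minimum. Clustering of deep sites would raise these figures, but the documents give no site counts.

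A reader might go further and infer that many enrolled patients lacked a pair, that power fell to 66% or 40%, or that the comparison is biased. The documents support none of these. They do not say that any patient lacked a pair. The large power losses require the full gap to reach the outcome, although change and PD reduction are analysed. And the coin flip makes a mismatch equally likely to favour either treatment, provided that the pair is fixed first.

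**Conclusion.** The point holds as a mismatch between the entry rule and the design: a patient can be eligible as written without a contralateral pair in which both sites reach 6 mm. What is at risk is precision, balance at baseline and the number of usable pairs.

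The loss cannot be sized from the documents, because the share of affected patients, the baseline gap, the correlation and the carry-through are all assumed. With correlation 0.5, a quarter of pairs mismatched and half the gap carried through, power stays above the planned 80% even at 3 mm. It falls below 80% only under harsher assumptions, such as no within-patient correlation with a 3 mm gap, full carry-through of 2 mm or more, or 40% of patients without a usable pair. This is a cheap improvement and does not by itself undermine the trial's conclusions.

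**What to change.** Reconcile Inclusion criteria with Clinical protocol in three steps:

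- Require at least one site that meets the existing PD threshold on each of the two contralateral sides.
- State that the study pair is chosen and recorded before the coin flip, and by what rule when a side has several qualifying sites.
- In the comparisons of PD reduction and CAL, include the site's own baseline value as a covariate: PD for PD reduction, CAL for CAL. The mixed models already carry baseline as one of the five time points, so the covariate belongs in these comparisons.

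Much of the text is in the past tense. If enrolment is complete, the entry rule cannot be changed. The sponsor can still state the pairing rule that was used, tabulate baseline PD by paired site, and apply the covariate.

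The cost is a sentence or two in the eligibility and protocol text and one term in the analysis, using data already collected. The downside is that some screened patients without a qualifying site on each side would be excluded.
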